10.3.5 Exploratory Analyses

Logistic regression will be carried out to investigate if a change in immunocompetence that is defined by peripheral blood mononuclear cell (PBMC) assays and phenotyping over the course of the study treatment correlates with the response and/or treatment-related toxicity. Proportional hazard model will be used to evaluate its relationship with the PFS. Similar exploratory analyses will be performed for evaluate potential correlations between immune infiltrates profiles (and expansion of specific clones) and clinical response.

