3 STUDY IMPLEMENTATION

3.1 STUDY DESIGN

This is a phase II study to evaluate the efficacy of treatment with nivolumab in glioma patients with or without HMP.

The study will be conducted in 2 stages.

During stage 1 of the study, 10 patients with HMP and 15 patients with NHMP will be accrued simultaneously into Cohorts 1 (HMP) and 2 (NHMP).

If 9 or more patients with HMP (Cohort 1) progress by 6 months, the Cohort 1 will be terminated early; otherwise, additional 19 patients will be accrued in stage II, resulting in a total sample size of 29.

If 3 or more patients with NHMP (Cohort 2) are progression-free at 6 months, the Cohort 2 will be moved to stage II and additional 15 patients will be accrued, resulting in a total sample size of 30.

All patients will be treated with nivolumab at a flat dose of 240 mg intravenously every 2 weeks (+/- 3 days) for cycles 1 through 2, then at a flat dose of 480 mg every 4 weeks for cycles 3-16. Treatment will be discontinued after 20 treatments given within 64 weeks.

One cycle is 4 weeks (+/- 3 days).

Study assessments presented in the Study Calendar (Section [3.5](#)).

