6 DATA COLLECTION AND EVALUATION

6.1 DATA COLLECTION

The PI will be responsible for overseeing entry of data into a 21 CFR Part 11-compliant data capture system provided by the NCI CCR and ensuring data accuracy, consistency and timeliness. The principal investigator, associate investigators/research nurses and/or a contracted data manager will assist with the data management efforts. Primary and final analyzed data will have identifiers so that research data can be attributed to an individual human subject participant.

All adverse events, including clinically significant abnormal findings on laboratory evaluations, regardless of severity, will be followed until return to baseline or stabilization of event. Document AEs from the first study intervention, Day 1 through 100 days after the study intervention was last administered. Beyond 100 days after the last intervention, only adverse events which are serious and related to the study intervention need to be recorded.

An abnormal laboratory value will be recorded in the database as an AE only if the laboratory abnormality is characterized by any of the following:

- Results in discontinuation from the study
- Is associated with clinical signs or symptoms
- Requires treatment or any other therapeutic intervention
- Is associated with death or another serious adverse event, including hospitalization.
- Is judged by the Investigator to be of significant clinical impact

If any abnormal laboratory result is considered clinically significant, the investigator will provide details about the action taken with respect to the test drug and about the patient's outcome.

Grade 1 AEs will not be collected.

All deaths will be recorded.

End of study procedures: Data will be stored according to HHS, FDA regulations, and NIH Intramural Records Retention Schedule as applicable.

Loss or destruction of data: Should we become aware that a major breach in our plan to protect subject confidentiality and trial data has occurred, this will be reported expeditiously per requirements in section [7.2.1](#)

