8.2 ASSESSMENT OF SAFETY EVENTS

AE information collected will include event description, date of onset, assessment of severity and relationship to study product and alternate etiology (if not related to study product), date of resolution of the event, seriousness and outcome. The assessment of severity and relationship to the study product will be done only by those with the training and authority to make a diagnosis and listed on the Form FDA 1572 as the site principal investigator or sub-investigator. AEs occurring during the collection and reporting period will be documented appropriately regardless of relationship. AEs will be followed through resolution.

SAEs will be:

- Assessed for severity and relationship to study product and alternate etiology (if not related to study product) by a licensed study physician listed on the Form FDA 1572 as the site principal investigator or sub-investigator.
- Recorded on the appropriate SAE report form, the medical record and captured in the clinical database.
- Followed through resolution by a licensed study physician listed on the Form FDA 1572 as the site principal investigator or sub-investigator.

For timeframe of recording adverse events, please refer to section **6.1**. All serious adverse events recorded from time of the first investigational product administration must be reported to the sponsor.

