10.3.3 Safety Analyses

The type and grade of AE will be summarized using frequency tables.

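### The exploratory logistic model for treatment-related toxicity (section 10.3.5) ignores time at risk, which depends on progression, so a marker change strongly tied to longer PFS can look tied to toxicity

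*Combined protocol and SAP*

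**What the plan says.** Section 10.3.5 states: "Logistic regression will be carried out to investigate if a change in immunocompetence", defined by PBMC assays and phenotyping, "over the course of the study treatment correlates with the response and/or treatment-related toxicity". A proportional hazards model is named there only for PFS. Neither a grade threshold nor a time window is given for toxicity, and there is no offset, exposure term or time-to-event method. Section 10.3.3 adds none: "The type and grade of AE will be summarized using frequency tables".

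Four other parts of the protocol determine how long a patient is observed for toxicity.

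- Section 3.1: "Treatment will be discontinued after 20 treatments given within 64 weeks".
- Section 3.7.1 makes progressive disease a criterion for removal from therapy.
- Section 6.1: "Document AEs from the first study intervention, Day 1 through 100 days after the study intervention was last administered". After that, only serious related events are recorded. Grade 1 events are not collected at all.
- Section 3.5, footnote 8: research blood is drawn before cycles 1, 2, 3, 5 and every second cycle to 15, or until progression, and also at treatment discontinuation.

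**The concern.** Logistic regression on whether a toxicity ever occurred treats each patient as having had the same opportunity to show one. Here the opportunity is set largely by time to progression. A marker change associated with longer PFS is then associated with a longer window, and through it with ever having a recorded toxicity, even if it has no effect on the toxicity rate.

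Linking immunocompetence to treatment-related toxicity is a stated exploratory objective (section 1.1.3). The planned model cannot separate a marker of toxicity from a marker of longer treatment. The trial could report that the immune change seen in patients who benefit also goes with harm, when those patients were simply treated and observed for longer.

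**Working it through.** **1. Treatment length.** Section 3.1 gives 16 cycles of 4 weeks: 16 × 4 = 64 weeks, which reproduces the stated figure. In the Study Calendar, day 1 of cycle 16 falls 15 × 4 = 60 weeks after the first dose. (The calendar's infusion days give 2 × 2 + 14 = 18 infusions where section 3.1 states 20. Those passages must be reconciled, but the 64 weeks is unaffected.)

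**2. Length of the AE window.** Window = week of last dose + 100/7 = week of last dose + 14.3. Section 10.1.1 cites median PFS of 9 weeks (glioblastoma) and 13 weeks (anaplastic astrocytoma). The first on-treatment MRI is at week 8.

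| Case | Last dose (week) | Window (weeks) | Full course ÷ this |
|---|---|---|---|
| Full course | 60 | 74.3 | 1.0 |
| Progression near week 13 | 12 | 26.3 | 2.8 |
| Progression near week 9 | 8 | 22.3 | 3.3 |
| Progression at week 8 | 6 | 20.3 | 3.7 |
| One infusion only | 0 | 14.3 | 5.2 |

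In simulated cohorts the ratio of the 90th to the 10th percentile of the window is 2.5 to 3.4.

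**3. Size of the bias.** The documents give no hazard shape or marker effect, so these are assumptions shown as ranges: N = 59; exponential PFS with median 11 weeks (between 9 and 13); progression found at 8-weekly MRI; the 100-day tail counted; a marker that affects PFS only; two-sided 5% Wald tests.

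| PFS HR per SD | Toxicity hazard | Logistic OR per SD | Logistic rejection |
|---|---|---|---|
| 0.8 | constant or front-loaded | 1.05–1.12 | 4.3–6.4% |
| 0.7 | constant | 1.14–1.18 | 6–10% |
| 0.5 | constant | 1.30–1.37 | 13–18% |
| 0.7 and 0.5 | front-loaded (Weibull shape 0.5) | 1.06–1.18 | 4–6% |
| 0.4 | constant | 1.44–1.53 | 15.2–27.5% |
| 0.4 | front-loaded | 1.19–1.23 | 5.6–10.4% |

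The rows for 0.8 and 0.4 use toxicity risks of 15, 35 and 57% by week 26. The 57% is the any-grade nivolumab figure in section 1.2.4, so it is an upper bound here because Grade 1 is not collected. In the runs covering 0.8, 0.6 and 0.4, a Cox model for time to first toxicity gave a median HR of 0.98 to 1.02 and rejected in 3.5 to 5.9% of trials.

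**4. Does a time-to-event model suit the planned marker?** The Cox result in step 3 is for a marker known at the start. The planned predictor is a later change, and section 3.3 takes patients off therapy for many toxicities, so toxicity itself can decide when the change is measured. Runs with a drifting marker unrelated to toxicity (0.5 to 2 SD per 26 weeks, assumed), measured at end of treatment and entered as fixed from first dose, gave:

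| Share of on-treatment toxicities that stop therapy | Cox rejection (HR) | Logistic rejection |
|---|---|---|
| None | 4–6% | 4–24% |
| Half | 6–18% (0.77–0.92) | 4–7% |
| All | 9–71% (0.59–0.86) | 4–12% |

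A Cox model from first dose with an end-of-treatment change can therefore be worse than the planned logistic model, in the opposite direction. A landmark Cox model at week 8 gave HR 0.95 to 1.05 and rejection of 2 to 6% in every setting examined.

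**The case against.** The strongest defence is that this is a hypothesis-generating correlation in at most 59 patients, and no decision rule or primary or secondary endpoint uses it. The 100-day tail applies to everyone and narrows the spread in windows. Sections 6.3.2 and 6.3.4 allow treatment past first imaging worsening, which loosens the tie between PFS date and exposure. Section 3.3 notes that rash tends to come early, and early toxicity shrinks the bias. All of this stands, and it limits the size and the stakes. It does not supply the missing allowance for time at risk.

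A reader might also infer more than the documents support:

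- That time at risk generally varies five-fold or more. The 5.2 is one infusion against the full course. Ratios of treatment time alone (64/13 = 4.9 to 64/8 = 8.0) leave out the 100-day tail that section 6.1 requires.
- That any marker predicting PFS will appear to predict toxicity. At HR 0.8 the test is near nominal.
- That the immune infiltrate analysis is affected. Sections 1.1.3 and 10.3.5 relate infiltrates to response, not toxicity.
- That the trial would claim causation. The plan speaks only of correlation.
- That a Cox model from first dose is a cost-free replacement. Step 4 of the working shows otherwise for a change measured later.

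**Conclusion.** The concern holds for the PBMC-toxicity analysis in section 10.3.5, and only there. Time at risk depends on PFS and typically varies about 3-fold, and the planned model ignores it. With a constant toxicity hazard and a PFS hazard ratio of 0.7 to 0.5 per SD, the spurious odds ratio is about 1.15 to 1.4 per SD and a nominal 5% test rejects in about 6 to 18% of trials. With a weak marker the distortion is negligible. With front-loaded toxicity it is small unless the marker is very strong (up to 10.4% rejection at HR 0.4).

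These sizes rest on the assumed PFS distribution, toxicity hazard and marker strength, none of which the documents state. That toxicity enters as a yes/no outcome is inferred from the choice of logistic regression. The direction follows from the protocol's own stopping and AE-recording rules. The correction is worth making because it is cheap, not because a main conclusion depends on it.

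**What to change.** In section 10.3.5, split toxicity from response.

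- **Event:** first treatment-related AE of Grade 2 or higher, since Grade 1 is not collected.
- **Model:** cause-specific proportional hazards for time to that event, censoring at 100 days after the last dose or at death.
- **Marker:** name one of two forms in advance. Either use a landmark, for example the change from pre-cycle 1 to pre-cycle 3, with follow-up starting at cycle 3 day 1 in patients still free of the event; or use a time-varying covariate that takes only values drawn before the time being assessed. Do not enter a later-measured change as if it were fixed from first dose.
- **Logistic regression:** keep it for response only.

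The cost is SAP wording. Section 8.2 already provides the timing ("AE information collected will include event description, date of onset"), and the pre-cycle 1 and pre-cycle 3 draws are already in the Study Calendar. The landmark form drops patients and toxicities before cycle 3, so it loses some events. The time-varying form avoids that loss with slightly more analysis work. Adding exposure as a covariate in the logistic model is not a substitute, because toxicity itself shortens exposure.

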11 COLLABORATIVE AGREEMENTS

11.1 AGREEMENT TYPE

The investigational study agent is provided by Bristol-Myers Squibb under a Clinical Trial Agreement (#1097).

12 HUMAN SUBJECTS PROTECTIONS

12.1 RATIONALE FOR SUBJECT SELECTION

This study was designed to include women and minorities but was not designed to measure differences of intervention effects. Males and females will be recruited with no preference to gender. No exclusion to this study will be based on race. Minorities will actively be recruited to participate.

12.2 PARTICIPATION OF CHILDREN

Children (younger than 18 years) will not be included in this protocol due to the limited data on nivolumab in children and the different biology of childhood malignancy.

12.3 PARTICIPATION OF SUBJECTS UNABLE TO GIVE CONSENT

Adults unable to provide consent are excluded from enrolling in the protocol. However, it is possible that subjects enrolled in the protocol may permanently lose the capacity to consent for themselves during the course of this study. For subjects that lose the ability to consent due to tumor progression, they will be taken off treatment but will have the opportunity to remain on study in long term follow-up for collection of outcomes for overall survival. If the reason for incapacity is due to a reason other than definitive disease progression and they are felt to be responding to the treatment under study, they will have the opportunity to continue this therapy if they have a LAR to provide ongoing consent.

All subjects \geq age 18 will be offered the opportunity to fill in their wishes for research and care, and assign a substitute decision maker on the “NIH Advance Directive for Health Care and Medical Research Participation” form so that another person can make decisions about their medical care in the event that they become incapacitated or cognitively impaired during the course of the study.

Note: The PI or AI will contact the NIH Ability to Consent Assessment Team (ACAT) for evaluation to assess ongoing capacity of the subjects and to identify an LAR, as needed.

Please see section [**12.8**](#) for consent procedure.

12.4 EVALUATION OF BENEFITS AND RISKS/DISCOMFORTS FOR ALL PARTICIPANTS

12.5 BENEFITS

The study drug may help to control the disease. Future patients may benefit from what is learned. There is no data for this treatment in the recurrent glioma with hypermutated phenotype. The condition has never been studied in the clinical studies. The research is likely to yield generalizable knowledge about the efficacy of nivolumab in this rare condition.

12.6 RISKS

12.6.1 Risks from Study Drug

The primary risk to patients participating in this research study is from the toxicity of nivolumab. Nivolumab is an investigational agent in the treatment of IDH mutated gliomas. The protocol provides for detailed and careful monitoring of all patients to assess for toxicity. Toxicity data will be collected and reviewed to ensure that there were no severe toxicities that would preclude further

patient enrollment. Patients will be treated with therapeutic intent and response to the therapy will be closely monitored.

12.6.2 Blood Collection

Risks of blood draws include pain and bruising in the area where the needle is placed, lightheadedness, and rarely, fainting. When large amounts of blood are collected, low red blood cell count (anemia) can develop.

12.6.3 Imaging

Subjects receive brain MRIs. People are at risk for injury from the MRI magnet if they have some kinds of metal in their body. It may be unsafe for subjects to have an MRI scan if they have pacemakers or other implanted electrical devices, brain stimulators, some types of dental implants, aneurysm clips (metal clips on the wall of a large artery), metal prostheses (including metal pins and rods, heart valves, and cochlear implants), permanent eyeliner, tattoos, an implanted delivery pump, or shrapnel fragments. Welders and metal workers may have small metal fragments in the eye. Subjects will be screened for these conditions before having any MRI scan. In addition, all magnetic objects (like watches, coins, jewelry, and credit cards) must be removed before entering the MRI scan room.

People with fear of confined spaces may become anxious during an MRI. Those with back problems may have back pain or discomfort from lying in the scanner. The noise from the scanner is loud enough to damage hearing, especially in people who already have hearing loss. Everyone having a research MRI scan will be fitted with hearing protection.

Scans may include the risks of an allergic reaction to the contrast. Participants might experience hives, itching, headache, difficulty breathing, increased heart rate and swelling. Participants undergoing gadolinium enhanced MRIs may also be at risk for kidney damage.

12.6.4 Electrocardiogram

Some skin irritation can occur where the ECG/EKG electrodes are placed. The test is completely painless, and generally takes less than a minute to perform.

12.6.5 Other Risks

Risks include the possible occurrence of any of a range of side effects which are listed in the Consent Document or this protocol document. Frequent monitoring for adverse effects will help to minimize the risks associated with administration of the study agents.

12.6.6 Questionnaires risks

Questionnaires may contain questions that are sensitive in nature.

12.6.7 Non-Physical Risks of Genetic Research

12.6.7.1 Risk of receiving unwanted information

Anxiety and stress may arise as a result of the anticipation that unwanted information regarding disease related DNA sequencing or disease tendencies, or misattributed paternity. Patients will be clearly informed that the data related to DNA sequencing and genetic analysis is coded, investigational and will not be shared with patients, family members or health care providers.

12.6.7.2 Risk related to possibility that information may be released

This includes the risk that data related to genotype, DNA sequencing or risk for disease tendency or trait can be released to members of the public, insurers, employers, or law enforcement agencies. Although there are no plans to release results to the patients, family members or health care providers, this risk will be included in the informed consent document.

12.7 RISKS/BENEFITS ANALYSIS FOR ALL PARTICIPANTS

This study is for patients with glioma. Currently, no successful standard therapy has been established, and the impact of chemotherapy at recurrence has been limited. Participants may obtain better responses with nivolumab.

The primary risk to patients participating in this research study is from the toxicity of nivolumab, that will be closely monitored.

Furthermore, we believe that genetic analyses planned for both normal and malignant tissues will pose no more than a minimal risk to the patients or their family members, as the results will not be reported with any identifiable information. The codes linking the subject with samples will be maintained by the principal investigator and research coordinator in a locked electronic data base, with access only to the PI and research coordinators. The testing will be considered exploratory and investigational, and without clinical utility. Results of these tests will not be shared with participants. There will be data monitoring plan to ensure the safety of the subjects.

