5.6 SAMPLES FOR GENETIC/GENOMIC ANALYSIS

5.6.1 Description of The Scope of Genetic/Genomic Analysis

Tumor and blood or saliva specimens will be collected, and genomic analyses will be performed. Tumor genetic material will undergo evaluation for whole exome sequencing and RNA sequencing

evaluating for possible neoantigens and to provide the immunologic microenvironmental landscape respectively. Genetic material containing germline DNA, including blood or saliva will be obtained for whole exome sequencing, which will be performed to combine with WES data from tumor tissue to identify tumor specific somatic mutations and neoantigens.

The genomic tests to determine the mutation burden are going to be performed by CLIA laboratories including Laboratory of Pathology and Genetic Branch. Formalin fixed, and paraffin embedded (FFPE) tumor tissue will be used for genomic material extraction. The whole exome sequencing will be performed to generate the tumor mutation burden from the non-synonymous mutations. Tumor genomic analysis will not be repeated if already performed on another NIH protocol.

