5.6.2 Management of Results

Subjects will be contacted if a clinically actionable gene variant is discovered. For the purpose of this study, clinically actionable findings are defined as disorders appearing in the American College of Medical Genetics and Genomics recommendations for the return of incidental findings that is current at the time of primary analysis. (A list of current guidelines is maintained on the CCR intranet: <https://ccrod.cancer.gov/confluence/display/CCRCRO/Incidental+Findings+Lists>. Subjects will be contacted at that time with a request to provide a blood sample to be sent to a CLIA certified laboratory.

5.6.3 A Certificate of Confidentiality will be obtained for the study as described in section 13.4

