5.6.4 Genetic Counseling

If the research findings are verified in the CLIA certified lab, the subject will be offered the opportunity to come to NIH (at our expense) to have genetic education and counseling with the NCI Genetics Branch to explain this result. If the subject does not want to come to NIH, a referral to a local genetic healthcare provider will be provided (at their expense). This is the only time during the course of the study that incidental findings will be returned. No interrogations regarding clinically actionable findings will be made after the primary analysis.

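### Section 12 says without exception that genetic results will not be shared with participants, but section 5.6 provides for returning clinically actionable findings

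*Combined protocol and SAP*

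**What the plan says.** Section 5.6 sets out how genetic findings are handled.

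- **5.6.1** plans germline as well as tumour sequencing: "Genetic material containing germline DNA, including blood or saliva will be obtained for whole exome sequencing".
- **5.6.2** commits to contact: "Subjects will be contacted if a clinically actionable gene variant is discovered". Actionable is defined by the American College of Medical Genetics and Genomics list in force at the primary analysis. The next step is confirmation: "Subjects will be contacted at that time with a request to provide a blood sample to be sent to a CLIA certified laboratory".
- **5.6.4** offers genetic counselling at NIH once the finding is verified, or referral to a local genetics provider. It adds: "This is the only time during the course of the study that incidental findings will be returned".

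Section 12 describes the same testing to a different effect.

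- **12.6.7.1** requires that patients be "clearly informed that the data related to DNA sequencing and genetic analysis is coded, investigational and will not be shared with patients". The same sentence also rules out sharing with family members and health care providers.
- **12.6.7.2** says that "there are no plans to release results to the patients, family members or health care providers".
- **12.7**, speaking of analyses of both normal and malignant tissue, says: "The testing will be considered exploratory and investigational, and without clinical utility". It then says: "Results of these tests will not be shared with participants".

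**The concern.** The protocol gives two incompatible accounts of whether a participant can learn a genetic result from this study. Staff who find a variant would ordinarily follow 5.6, which is the specific procedure, so the main weakness is in disclosure. Section 12.6.7.1 directs what patients are to be told, and followed as written it has them told that nothing will come back.

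Two consequences follow. The section devoted to the risk of unwanted information omits the one planned route by which such information would reach a participant, namely being contacted about a hereditary finding. And 12.7 rests its judgement of minimal risk, for patients and their families, partly on results not being reported in identifiable form. Contacting a particular participant about a variant departs from that premise.

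**Working it through.** The plan states no figure on this point, so the check is a comparison of texts.

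**1. Do the two parts cover the same tests?** Yes. Section 5.6.1 covers germline exome sequencing from blood or saliva together with tumour sequencing. Section 12.7 covers normal and malignant tissue. Section 12 therefore cannot be read as limited to tumour assays.

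**2. Do they conflict?**

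| Question | Section 5.6 | Section 12 |
|---|---|---|
| Is the participant contacted about a finding? | Yes, if actionable (5.6.2) | Data and results not shared (12.6.7.1, 12.7) |
| Is a result returned? | Yes, once verified (5.6.4) | No (12.7); no plans to (12.6.7.2) |
| Can a health care provider be involved? | Yes, by referral (5.6.4) | Data not shared with providers (12.6.7.1) |
| Can a result matter clinically? | Yes, by the definition of actionable (5.6.2) | No clinical utility (12.7) |

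**3. Does section 12 contain an exception?** No. None of the three subsections excepts actionable findings or refers to 5.6, and neither does the rest of section 12.

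**4. Would it help to say that only the CLIA-confirmed result is returned?** No. Under 5.6.2 the research finding triggers the contact, before confirmation. Section 5.6.4 itself describes incidental findings as being returned.

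**5. How many participants might this touch?** The documents give no carrier rate, so the rates q below are assumptions chosen only to show a range. With n patients sequenced, the expected number of cases is n × q and the chance of at least one is 1 − (1 − q)^n. The first n is the maximum of 59 treated patients (section 10.1.1.1). The second is 40: the HMP cohort stopped after 10 and the NHMP cohort completed at 30 (section 10.1.1).

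| q (assumed) | Expected, n = 59 | At least one, n = 59 | Expected, n = 40 | At least one, n = 40 |
|---|---|---|---|---|
| 1% | 0.59 | 1 − 0.99^59 = 0.447 | 0.4 | 1 − 0.99^40 = 0.331 |
| 2% | 1.18 | 1 − 0.98^59 = 0.696 | 0.8 | 1 − 0.98^40 = 0.554 |
| 5% | 2.95 | 1 − 0.95^59 = 0.952 | 2.0 | 1 − 0.95^40 = 0.871 |

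The chance that no case arises is thus 55%, 30% or 5% with 59 patients, and 67%, 45% or 13% with 40.

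**The case against.** The best reply is that section 12 states a general rule for coded research data, while 5.6 is a narrow exception: limited to a published list, confirmed in a CLIA laboratory, and applied once. On that reading there are not two rival procedures, only a rule whose exception is stated elsewhere. This is fair as a description of how staff would act. It does not rescue 12.6.7.1, which governs what patients are told and states the rule alone.

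A second reply is that participants rely on the consent form, which is IRB-approved and was not among the documents reviewed, and that section 12.8 has an investigator explain the tests. This stands as a limit on the finding. A correct form would still conflict with 12.6.7.1, so the protocol text needs correcting either way.

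Three smaller points also stand:

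- Section 12.6.7.1 does name anxiety about unwanted genetic information as a risk; what it lacks is the route.
- Section 12.6.7.2 is mainly about release to outsiders such as insurers and employers, so it is the weakest of the three instances.
- The carrier rates have no source in the documents, and the number sequenced could differ from 59. The accrual ceiling is 70 and mutation burden is tested at screening. On the other side, tumour analysis already done on another NIH protocol is not repeated, and the study calendar to which section 5.1 refers for germline sampling shows no row for it. The probabilities are illustrative and carry no weight in the conclusion.

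**Conclusion.** The concern holds. Sections 12.6.7.1 and 12.7 contradict section 5.6, and 12.6.7.2 has the same gap in weaker form. Read alone, 12.7 would withhold an actionable hereditary result that 5.6 requires to be followed up. The conclusion rests on the wording alone and on no assumed rate; how many participants it would reach remains unknown. It should be corrected because it bears on disclosure to participants and is cheap to put right. It has no bearing on the validity of the trial's efficacy results.

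**What to change.** Leave section 5.6 as the governing policy and bring section 12 into line with it:

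- In 12.6.7.1, 12.6.7.2 and 12.7, add: *except clinically actionable findings returned as described in section 5.6*.
- In 12.7, qualify the statement that the testing lacks clinical utility in the same way.
- In 12.6.7.1, add a sentence saying that a participant may be contacted about a hereditary finding.
- Check that the consent form says the same.

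The cost is a few lines of text and a consent-form check at the next amendment. Procedures, data collection and analysis do not change.
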